##### 3.1.4 Dose Limiting Toxicity (DLT) Criteria

A potential DLT is defined as any of the following EXT608 TEAEs that occurs during the DLT period, graded according to the NCI Common Terminology Criteria for Adverse Events (CTCAE), Version 5.0 (2):

- Grade = 3 TEAE
- Grade = 3 anemia
- Grade = 3 AST/ALT elevation; and/or
- Grade = 2 AST/ALT elevation and Grade = 2 Bilirubin elevation

- Grade = 3 QTc prolongation
- Grade = 3 Hyper- and/or Hypotension
- Grade = 2 Hyperparathyroidism
- Grade = 2 Hyperthyroidism
- Grade = 3 Hypercalcemia
- Grade = 3 Hypocalcemia
- Grade = 3 Hypophosphatemia
- Grade = 3 Hypomagnesemia
- Grade = 3 Creatinine increased

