### 3.3.4 Safety Variables

#### 3.3.4.1 *Adverse Events (AE)*

All observed or volunteered adverse events regardless in the treatment group or suspected causal relationship to the investigational device are captured in the EDC.

For all AEs, reformatting maybe applied and necessary transformation/Substitution may be needed as specified below:

- If an AE has known onset date but unknown onset time, then 12:00 will be used to substitute the onset time
  - The purpose of this substitution is for the determination of the TEAE
- If an AE has unknown onset date, no substitution will be done.

Treatment-emergent adverse event (TEAE) is defined as a post-baseline adverse event with onset date and time after the initiation of study treatment.

- Baseline is the IP administration date and time
- In this study, TEAE are the AEs that occur after the first successful IP administration.
  - If the AE has an unknown onset date, it will be assumed to be non-TEAE unless the investigational site confirms it is an TEAE

AE Coding:

- AE will be coded with latest available, at the time of coding, MedDRA code.

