#### **3.4.5.1 Adverse Event**

All AE (including TEAE and non-TEAE) will be listed.

Unless there are less than or equal to 5 TEAE in the whole study period, TEAE will be summarized as followed:

All TEAE will be presented with the number and percentage of participants and events (counts only), by System organ class (SOC) and by Preferred Term (PT).

The same summary will also be presented for the following group:

- All TEAE that may have a relationship to the study medication (i.e., site categorize the relationship in EDC as either Related, Probable, Possible, or Unlikely)
- Intensity Categorization Groups: Mild, Moderate and Severe
- Serious TEAE (SAE)

An overview of the above summary with count and percentage of participants will also be provided.

Any non-TEAE will be provided as listing only.

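### The SAP counts an adverse event with an unknown onset date as not treatment-emergent by default, which under-counts TEAEs in a first-in-human safety study

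*SAP*

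**What the plan says.** SAP 3.3.4.1 defines treatment emergence by onset relative to the injection: "In this study, TEAE are the AEs that occur after the first successful IP administration". It then deals with missing onset information in two ways.

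- **Date known, time unknown:** noon is substituted, for the stated purpose of deciding TEAE status.
- **Date unknown:** "If an AE has unknown onset date, no substitution will be done", and "If the AE has an unknown onset date, it will be assumed to be non-TEAE unless the investigational site confirms it is an TEAE".

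The section has no rule for partial dates and makes no use of the resolution date.

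SAP 3.4.5.1 sets out the reporting. Every event is listed: "All AE (including TEAE and non-TEAE) will be listed". The summaries by system organ class and preferred term, relationship, intensity and seriousness cover TEAEs only. For the rest, "Any non-TEAE will be provided as listing only". The summaries also depend on a count: "Unless there are less than or equal to 5 TEAE in the whole study period, TEAE will be summarized as followed".

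Protocol 2.1 and SAP 1.2.1 make the incidence, nature and severity of adverse events from Day 0 to Day 28 the first measure under the primary objective.

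**The concern.** When the onset date of an event is missing, the analyst must place it before or after dosing without the one fact that decides the matter. This SAP places it before dosing unless someone positively shows otherwise. For a first-in-human study whose primary objective is safety, that is the less cautious direction. The uncertain events leave the counted tables, and reported TEAE incidence can fall below its true value but not rise above it through this rule.

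The protocol contains a plausible route to such events. Under Protocol 6.3.1 and 6.3.2, the complete physical exam is done at screening and at the last visit, and exams in between are directed by symptoms. A new finding at the last visit is recorded as an adverse event. If it caused no symptoms, neither participant nor site may know when it began, and the site may be unable to confirm that it followed the injection. The default then removes it from the summaries. The intervals between the Day 7, 14, 21 and 28 visits leave some room for undated events too.

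The SAP is also uneven here. It supplies a rule for the smaller gap, a missing clock time, and settles the larger gap by exclusion.

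**Working it through.** **Inputs**

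- Adverse events are collected from consent to the follow-up or early termination visit (Protocol 6.10.1.1).
- Screening falls within 28 days of dosing; follow-up visits run to Day 28 (Protocol 3.1.6).
- The synopsis gives a 4-week screening period, about 5 inpatient days and 25 outpatient days, about 58 days in total.
- Each cohort has 3 active participants and 1 placebo participant, with up to 6 cohorts (Protocol 3.1.1). Placebo is pooled (Protocol 8.3).
- TEAE summaries are produced only above 5 TEAEs (SAP 3.4.5.1).

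**Step 1: the plan's own figure.** 28 + 5 + 25 = 58 days, as stated.

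**Step 2: could an undated event be post-dose?** The documents do not say how undated events fall around dosing. As a rough guide, assume a constant event rate, 28 days of follow-up and *s* days from consent to dose. The post-dose share of collection time is 28 / (28 + *s*).

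| *s* (days) | Calculation | Share |
|---|---|---|
| 28 | 28/56 | 50% |
| 21 | 28/49 | 57% |
| 14 | 28/42 | 67% |
| 7 | 28/35 | 80% |
| 2 | 28/30 | 93% |

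At the 28-day limit, the 2-day tolerance on the Day 28 visit gives 26/54 = 48% to 30/58 = 52%. A doubled event rate after dosing would give 56/84 = 67% there. Actual screening lengths are not stated. These shares describe all undated events, before any site confirmation. They support saying that an undated event may well be post-dose, and no more than that.

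**Step 3: effect of one omitted event on the proportion with any TEAE.** This is the worst case, in which the participant has no other TEAE.

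- Dose group of 3: 1/3 = 33.3 points.
- Pooled placebo over six full cohorts, 6 × 1 = 6: 1/6 = 16.7 points.
- All active participants over six full cohorts, 6 × 3 = 18: 1/18 = 5.6 points.

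If the participant has another TEAE, the any-TEAE proportion does not move. Only individual rows (preferred term, intensity, relationship or seriousness) may change.

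**Step 4: the production threshold.** With 6 true TEAEs, one reclassified event leaves 6 − 1 = 5. Five does not exceed 5, so the summary tables are not produced.

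**The case against.** The strongest reply is that the rule will rarely operate and hides nothing. Protocol 6.10.1.1 asks for a date of first occurrence for every event and a query at every visit. Participants are in the unit from the day before dosing through at least 72 hours after it. The site can override the default, and every event is listed in a study of roughly 24 to 30 participants with no formal hypothesis testing. This stands as far as frequency goes: few events should be affected, and their number cannot be calculated. It does not defend the direction of the default. The override helps least where the site cannot date the event, and a listed event is visible but not counted.

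It can also be said that the SAP does not class a partial date as unknown, so an event dated to a month after the dosing month already meets the TEAE definition. That is fair. On partial dates the gap is one of clarity.

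A reader might infer four stronger things, which the documents do not support.

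- **That undated events are more likely than not post-dose.** At the longest permitted screening it is a tie, and shorter screening intervals are an assumption.
- **That the default is wrong in 50% to 93% of cases.** The shares in the working cover all undated events, whereas the rule acts only on those the site has not confirmed. The clearest post-dose events are the easiest to confirm, so the remainder is a selected group for which no rate can be derived.
- **That the rule can only flatter the drug.** It applies to placebo too, and dropping a placebo event makes the drug look relatively worse. Only absolute incidence is biased one way.
- **That an undated event could not be a dose-limiting toxicity.** Protocol 3.1.4 does say "A potential DLT is defined as any of the following EXT608 TEAEs that occurs during the DLT period", but it does not adopt the SAP's missing-date rule. The decision tree in Protocol 3.1.5 acts on related Grade 3 events, and board procedures are left to safety plans that were not supplied (Protocol 4.3.1.3, SAP 3.5).

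**Conclusion.** The point holds for absolute TEAE incidence. As written, the SAP excludes from all TEAE summaries any adverse event whose onset the site can neither date nor confirm as post-dose. For a first-in-human study whose first primary measure is adverse event incidence, this default is anti-conservative. It is a stated rule and not an omission of detail.

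The expected effect is small, because few events should lack an onset date, but it is not computable. The worst case is large because the groups are small: 33 points in a dose group of 3, if that participant has no other TEAE, or loss of the TEAE summaries if the study total drops from 6 to 5. The conclusion does not rest on the constant-rate assumption. It needs only that some undated, unconfirmed events may be post-dose.

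**What to change.** Reverse the default in SAP 3.3.4.1. After a site query, an adverse event with an unknown or partial onset date counts as a TEAE unless one of three things shows that it began before dosing: the known part of the onset date, the resolution date, or the site's own confirmation. State that partial dates fall under this rule. Footnote the TEAE tables with the number of events classified this way, so a reader can see how far the tables depend on it.

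The cost is a short amendment to one SAP subsection, the site queries and one footnote. The downside is that a few pre-dose events may be counted as TEAEs. The footnote gives the most that this could be, and for a first safety study it is the safer error.

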#### 3.3.4.2 *Vital Signs*

Change from baseline will be calculated for vital sign from Day 0 to Day 28.

- Baseline will be the vital signs collected at Day 0 -90 pre-dose
- If Day 0 -90min vital signs are missing, then the vital signs on Day -1 will be considered as baseline. If the vital sign on Day -1 is also missing, then the change from baseline will be set as missing.

#### 3.3.4.3 *ECG*

Change from baseline will be calculated for ECG from Day 1 to Day 3.

- Baseline will be the ECG collected at Day -1
- If Day -1 ECG is missing, then the ECG on Screening will be used as baseline.

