  - e. 6 months - fluoride tablets, oral bisphosphonates, methotrexate, growth hormone, digoxin, raloxifene or similar selective estrogen receptor modulators (SERMs)
  - f. 12 months - intravenous bisphosphonates
9. Participant is pregnant, nursing, or planning a pregnancy during the course of or within 3 months of completing this study.
10. Participant is male and intends to donate sperm before 90 days after study drug administration.
11. Participant has a history of cancer or other malignancy, with the exception of basal cell carcinoma that has been in remission for at least 5 years prior to Day -1.
12. Participant has a positive test result for hepatitis B surface antigen (HBsAg), hepatitis C virus (HCV) antibody or a human immunodeficiency virus (HIV) infection at Screening.
13. Participant has used nicotine-containing products (including but not limited to cigarettes, electronic cigarettes, pipes, cigars, chewing tobacco, nicotine patch or

nicotine gum) within 28 days prior to Inpatient Check-in (Day -1) or a positive urine cotinine test at Screening or Inpatient Check-in (Day -1).

14. Participant has poor peripheral venous access.
15. Participant has donated or lost 450 mL or more of their blood volume (including plasmapheresis) or had a transfusion of any blood product, within 45 days prior to Day 0.
16. Participant has a Screening or Inpatient Check-in (Day -1) abnormal (CS) ECG.  
Entry of any participant with an abnormal (NCS) ECG must be approved and documented by signature by the Investigator or medically qualified sub-investigator.
17. Participant has a resting blood pressure outside the ranges of 90 to 140 mm Hg for systolic and 55 to 90 mm Hg for diastolic, confirmed with repeat per Investigator discretion, at the Screening Visit or Inpatient Check-in (Day -1).
18. Participant has a resting heart rate outside the range 40 to 90 bpm, confirmed with repeat per Investigator discretion, at the Screening Visit or Inpatient Check-in (Day -1).
19. Participant has increased CV proarrhythmic potential (3):
  - a. Participant has a QT interval with Fridericia's correction method (QTcF) >450 ms (males) or >450 ms (females) or PR outside the range of 120 to 220 ms, confirmed with one repeat testing, at the Screening Visit or Inpatient Check-in (Day -1) Visit.
  - b. A history of additional risk factors for TdP (e.g., heart failure, hypokalemia, family history of Long QT Syndrome).

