## **6.7 Electrocardiogram (ECG)**

Equipment for recording the ECG should be recently serviced and calibrated. Machine calibration records and performance data should be maintained on file.

A standard 12-lead ECG will be obtained in supine position after at least 5 minutes at rest. A copy of the recording will be made available for the Sponsor.

At screening, any abnormalities or normal variants will be assessed for clinical relevance and recorded in the medical history. Subsequent changes will be recorded in the EDC description text field and deemed clinically relevant or not (separate files). Changes that are deemed clinically relevant are furthermore recorded as AEs.

In addition to the description above, the ECG intervals PR, QRS, RR and QT will be measured and recorded in the eCRF for QTc assessment.

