### 8.3 Data Analysis

AEs will be presented in listings and Treatment Emergent Adverse Events (TEAEs) will be summarized. Individual results of laboratory tests (hematology, chemistry, and urinalysis) will be listed and change from baseline will be summarized using shift tables. Individual results of vital signs will be listed and observed values and changes from baseline will be summarized.

Individual results of quantitative ECG parameters from the 12-lead safety ECGs will be listed and observed values and changes from baseline will be summarized and analyzed consistent with the ICH E14 (3).

All summaries will be performed by placebo and each EXT608 dose level. Placebo data will be pooled across cohorts. Physical exam findings will be presented in data listings.

Concentrations of EXT608 will be summarized by dose over each scheduled sampling time using descriptive statistics. Individual plasma concentration data versus time will be presented in a data listing. PK parameters will be summarized by dose using descriptive

statistics. Dose proportionality will be assessed graphically and using a power model. PD will be presented in listings and summarized by dose and time point.

Detection of ADA and NAbs will be presented in listings and summarized by dose and time point.

No formal hypothesis testing will be conducted as part of this study.

DMB data packages will be based on the FAS for safety and PP for PK/PD.

Further details are described in the Statistical Analysis Plan.

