## 1.2 OBJECTIVES

### 1.2.1 Primary Objective

The primary objective is to characterize the safety and tolerability profile of escalating dose levels of EXT608 when administered to healthy adult participants as a single injection as assessed by:

- Incidence, nature, and severity of adverse events (AEs) and withdrawals due to treatment emergent AEs (TEAEs) [Time Frame: Day 0 up to Day 28]
- Frequency and severity of post-dose change from baseline in hematology, serum chemistries, urinalysis, electrocardiogram (ECG), vital signs, and physical examination (Exam) findings [Time Frame: Day 0 up to Day 28]
- Percentage of participants with injection or infusion site reactions [Time Frame: Day 0 to Day 7]

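### SAP 3.3.4.3 limits ECG change from baseline to Days 1 to 3, against a primary objective that runs from Day 0 to Day 28, and the SAP text names no QTc variable

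*SAP*

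**What the plan says.** **Objective.** Protocol 2.1 and SAP 1.2.1 both list, among the primary safety assessments, post-dose change from baseline in "electrocardiogram (ECG), vital signs, and physical examination (Exam) findings [Time Frame: Day 0 up to Day 28".

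**SAP derivation.** SAP 3.3.4.3 reads: "Change from baseline will be calculated for ECG from Day 1 to Day 3". The reference value is also fixed there: "Baseline will be the ECG collected at Day -1", with the screening ECG as the fallback. SAP 3.4.5.4 presents ECG values at each time point and the change defined in 3.3.4.3, descriptively by arm.

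**Protocol analysis commitment.** Protocol 8.3 says of the quantitative ECG parameters that "observed values and changes from baseline will be summarized and analyzed consistent with the ICH E14 (3"). The same section closes: "Further details are described in the Statistical Analysis Plan". Protocol 6.7 says that "the ECG intervals PR, QRS, RR and QT will be measured and recorded in the eCRF for QTc assessment".

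**Other uses of QTc.** Protocol 4.2 excludes on "QT interval with Fridericia's correction method (QTcF) >450 ms", and Protocol 3.1.4 lists "Grade = 3 QTc prolongation" as a potential DLT.

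**Declared changes.** SAP 1.4 states that there are no modifications from the protocol's statistical section.

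**The concern.** The SAP rule is narrower than the objective it serves. The objective asks for change from baseline, and that is the quantity the SAP restricts. Vital signs stand in the same item of the objective with the same time frame, and SAP 3.3.4.2 gives them the full Day 0 to Day 28 window. If ECGs are taken in the hours after a first-in-human injection, or at the end of study, they would have no change score in a primary safety summary.

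The second gap is QTc. The protocol records the intervals in order to assess it and defers analysis detail to the SAP, but the SAP text defines no such variable. Without a named correction, two programmers could produce different ECG tables from the same SAP. A table of uncorrected QT, if that were what was produced, would mix heart-rate change with repolarisation change.

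**Working it through.** No figure in the plan needs to be reproduced. The check is a comparison of sections, followed by one short illustration of why the correction has to be named.

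**1. The windows side by side**

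| Item | Source | Window for change from baseline |
|---|---|---|
| Primary objective, ECG | Protocol 2.1; SAP 1.2.1 | Day 0 to Day 28 |
| Vital signs | SAP 3.3.4.2 | Day 0 to Day 28 |
| Physical exam | SAP 3.3.1 | Screening to Day 28 or end of study |
| ECG | SAP 3.3.4.3 | Day 1 to Day 3 |

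The study days named from dosing onward are 0, 1, 2, 3, 5, 7, 14, 21 and 28, nine in all. Days 1, 2 and 3 fall inside the ECG window. Day 0 and Days 5, 7, 14, 21 and 28 fall outside it. This describes the window only. It does not count lost ECGs, because the days with a scheduled ECG cannot be seen.

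**2. What the restriction removes**

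SAP 3.4.5.4 puts no day limit on observed values. An ECG outside Days 1 to 3 is therefore still summarised as observed. It loses its change from baseline, and 3.4.5.4 takes change from 3.3.4.3, so no later section restores it.

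**3. QTc in the two documents**

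- Protocol: QTcF is an eligibility variable (4.2), QTc prolongation is a potential DLT (3.1.4), PR, QRS, RR and QT are recorded for QTc assessment (6.7), and an ICH E14-consistent analysis is promised (8.3).
- SAP: a reading of the text finds no mention of QT, QTc, QTcF, Fridericia or E14. It does write out formulas for age (3.3.1.1), hourly urine volume (3.3.3.6), and normalised VAS and lesion area (3.3.4.5).

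**4. Why the correction must be named**

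Fridericia: QTcF = QT / RR^(1/3), so QT = QTcF × RR^(1/3), with RR = 60 / heart rate in seconds. Protocol 4.2 admits resting heart rates of 40 to 90 bpm. Take QTcF as constant at 400 ms; this value is an assumption for illustration and is not in the documents.

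- 40 bpm: RR = 60/40 = 1.5 s; QT = 400 × 1.5^(1/3) = 400 × 1.145 ≈ 458 ms.
- 90 bpm: RR = 60/90 = 0.667 s; QT = 400 × 0.667^(1/3) = 400 × 0.874 ≈ 349 ms.
- 60 to 75 bpm: RR goes from 1.0 to 0.8 s; QT goes from 400 to 400 × 0.928 ≈ 371 ms, a fall of about 29 ms with no change in QTcF.

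With three active participants per cohort, heart-rate shifts of that kind could hide or mimic an effect in a mean of uncorrected QT.

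**The case against.** **The window may simply mirror the ECG schedule.** The procedure tables and most of the day-by-day text in Protocol 7.2 are not shown, and the visible text places ECGs only at screening and Day -1. If post-dose ECGs are scheduled only on Days 1 to 3, no collected data are lost. This stands, and it is why the size is left open. It does not remove the mismatch: in that case the objective's ECG time frame needs reconciling instead.

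**Day 0 up to Day 28 is an outer frame for several assessments and does not require daily measurement.** This also stands. Physical exam shares the frame and is compared only from screening to Day 28 or end of study. Three days out of 28, or out of nine named days, is therefore no measure of loss.

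**ECGs outside the window are not ignored.** A reader might infer that they drop out of the primary safety analysis. The documents do not support that. Observed values are summarised at each time point (SAP 3.4.5.4), clinically relevant ECG changes are recorded as AEs (Protocol 6.7), and all AEs are listed (SAP 3.4.5.1).

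**QTc may be planned elsewhere.** A reader might infer that the SAP, followed literally, summarises uncorrected QT. That goes too far, because the SAP names no ECG parameter at all, corrected or not. QTc could arrive as a reported value, and the planned table list is a separate file that is not supplied (SAP 4). Potential DLTs are evaluated under a Safety Plan (Protocol 4.3.1.3), so the DLT entry does not itself show a gap in the final analysis. What remains is that Protocol 8.3 defers the detail to the SAP, and the SAP text defines no QTc variable or correction.

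**SAP 1.4 does not contradict the window.** It covers only the protocol's statistical section, and Protocol 8.3 sets no ECG day range. This is right: the statement of no modifications bears on the ICH E14 commitment only.

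**Conclusion.** The point holds on two counts.

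First, the Day 1 to Day 3 limit on ECG change conflicts with the Day 0 to Day 28 frame of the primary objective. Any post-dose Day 0 ECG, and any ECG after Day 3, would be left without a change from baseline. Whether that is none, a few or many is unknown from the public text, but either answer calls for an edit.

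Second, the SAP text names no QTc variable or correction, against a protocol that records the intervals for that purpose and commits to an ICH E14-consistent analysis.

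The trial is descriptive, with no hypothesis testing promised in Protocol 8.3. The consequence is incomplete or ambiguous reporting of one primary safety component, not a wrong error rate. The sponsor should correct it, although it does not threaten the trial's validity. The conclusion rests on the SAP text as supplied; an unseen table list that includes QTc would soften the second count but would not define the variable.

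**What to change.** 1. In SAP 3.3.4.3, calculate change from baseline for every post-dose ECG collected from Day 0 through Day 28 or early termination. This wording fits any schedule. If ECGs are in fact scheduled only on Days 1 to 3, reconcile the ECG time frame in the objective (Protocol 2.1, SAP 1.2.1) with that schedule instead.
2. In the same section, name QTcF as an analysed variable: QTcF = QT / RR^(1/3), RR in seconds. This is the correction the protocol already uses for eligibility, and QT and RR are already recorded.
3. In SAP 3.4.5.4, list the ECG parameters to be summarised, and present QTcF and its change from baseline by dose level and pooled placebo. State how this meets the ICH E14 commitment in Protocol 8.3, or record the departure in SAP 1.4.

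Categorical outlier tables are optional; with three active participants per cohort they add little to the individual listings. The cost is SAP wording and one derived variable, with no new procedures.
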